4.2.4. Choice of sample size

Taking into consideration the study primary objective, the study sample size with 40 treated subjects with a centrally confirmed *BRAF*^{V600E} mutation in stage 1, and 50 in stage 2 (if study does not stop for futility after stage 1), is considered sufficient to evaluate the antitumor activity of the study treatment (see **Section 13.3** for more details).

5. STUDY POPULATION

Subjects fulfilling all of the inclusion criteria and none of the exclusion criteria will be eligible.

5.1. INCLUSION CRITERIA

1. Provide a signed and dated informed consent document.
2. Male or female ≥ 18 years of age at time of informed consent.
3. Histologically or cytologically confirmed CRC that is metastatic and unresectable at time of study entry (i.e. not suitable for complete surgical resection at screening).
4. Presence of $BRAF^{V600E}$ mutation in tumor tissue previously determined by a local assay at any time prior to screening.

Notes:

- a. *Only PCR and NGS-based local assays results will be acceptable.*
 - b. *If at any time there is lack of confirmation of the $BRAF^{V600E}$ mutation in a total of 6 subjects ($\geq 6\%$ of the total targeted 90 treated subjects) or discordance between the local assay and the central laboratory in 3 subjects ($\geq 3\%$ of the total targeted 90 treated subjects), discordance or impossibility to confirm the $BRAF^{V600E}$ mutation in 3 subjects, all subsequent subjects will be required to have $BRAF^{V600E}$ determined by the central laboratory prior to study treatment assignment.*
 - c. *Central testing cannot be repeated to resolve discordances with a local result once the central laboratory delivers a definitive result (positive or negative).*
 - d. *If the result from the central laboratory is indeterminate or the sample is deemed inadequate for testing, additional samples should be submitted (archival material only).*
 - e. *If more than 1 discordant result from any local laboratory leads to subject enrollment, subsequent results from this local laboratory will not be accepted for further subject enrollment.*
5. Eligible to receive cetuximab per locally approved label with regards to tumor RAS status.
e.g.: In agreement with EU label, evidence of wild type RAS (KRAS and NRAS) in EU countries.
 6. Able to provide a sufficient amount of representative tumor specimen (primary or metastatic, archival or newly obtained) for testing of BRAF and RAS mutation status^(a).
(a) FFPE tumor tissue block or a minimum of 10 slides, optimally up to 15 slides.
 7. Evidence of measurable disease, as per RECIST 1.1.

Note: Lesions in areas of prior radiotherapy or other loco-regional therapies are considered measurable only if progression has been documented in the region following therapy.

8. Eastern Cooperative Oncology Group (ECOG) performance status 0 or 1.

9. Adequate bone marrow function at screening and baseline:

- i. Absolute neutrophil count (ANC) $\geq 1.5 \times 10^9/L$.*
- ii. Platelets $\geq 100 \times 10^9/L$.*
- iii. Hemoglobin ≥ 9.0 g/dL.*

Note: Blood transfusions are allowed provided that the subject has not received more than 2 units of red blood cells in the 4 weeks prior to achieve the minimum required hemoglobin level.

10. Adequate renal function at screening and baseline.

- i. Serum creatinine $\leq 1.5x$ upper limit of normal (ULN) or*
- ii. Calculated creatinine clearance (CrCl) ≥ 50 mL/min by Cockcroft-Gault formula*

11. Adequate electrolytes at screening and baseline, defined as serum potassium and magnesium levels within institutional normal limits.

Note: replacement treatment to achieve adequate electrolytes will be allowed

12. Adequate hepatic function at screening and baseline:

- i. Serum total bilirubin $\leq 1.5 \times$ ULN and < 2 mg/dL. Note: Total bilirubin $> 1.5 \times$ ULN is allowed if direct (conjugated) bilirubin is $\leq 1.5 \times$ ULN (and indirect (unconjugated) bilirubin is $\leq 4.25 \times$ ULN – Only applicable for France).*
- ii. Alanine aminotransferase (ALT) and/or aspartate aminotransferase (AST) $\leq 2.5 \times$ ULN, or $\leq 5 \times$ ULN in the presence of liver metastases.*

13. Adequate cardiac function at screening:

- i. Left ventricular ejection fraction (LVEF) $\geq 50\%$ as determined by MUGA scan or ECHO.*
- ii. Mean triplicate QT interval corrected for heart rate according to Fridericia's formula (QTcF) value ≤ 480 msec.*

14. Subject able to take oral medications.

15. Willing and able to comply with scheduled visits, treatment plan, laboratory tests and other study procedures.

16. Female subjects are either postmenopausal for at least 1 year, are surgically sterile for at least 6 weeks, or must agree to take appropriate precautions to avoid pregnancy.

Notes:

- (a) *Precautions to avoid pregnancy must be conducted from screening through 6 months after the last dose of cetuximab or through 30 days after the last dose of encorafenib or binimetinib, whichever is later if of childbearing potential.*
- (b) *Permitted methods of contraception as provided (in Section 5.3.1) should be communicated to the subjects and their understanding confirmed. For all females, the pregnancy test must be negative at screening and baseline.*

17. Male subject must agree to take appropriate precautions to avoid fathering a child.

Notes:

- (a) *from screening through 6 months after the last dose of cetuximab or through 90 days after the last dose of encorafenib or binimetinib, whichever is later.*
- (b) *permitted methods of contraception as provided (in Section 5.3.1) should be communicated to the subjects and their understanding confirmed.*

18. Subjects under guardianship or partial guardianship will be eligible unless prohibited by local laws or by local/central ethic committees.

Note: where allowed, all procedures prescribed by law must be followed.

19. Affiliated to a social security system, or is a beneficiary (if applicable in the national regulation).

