Asymptomatic absolute decrease of > 10% in LVEF compared to baseline and the LVEF is below the institution's LLN (e.g., a decrease of 60% to 48% is an absolute decrease of 12%)	Interrupt dosing of binimetinib and repeat evaluation of LVEF within 2 weeks. 
 If the LVEF recovers (defined as LVEF ≥ 50% or ≥ lower limit of normal (LLN) and absolute decrease ≤ 10% compared to baseline) ≤ 21 days, resume treatment at 1 reduced dose level^b of binimetinib after approval of the Sponsor's Medical Monitor. Monitor LVEF 2 weeks after resuming binimetinib, every 4 weeks for 12 weeks and subsequently as per protocol. If LVEF does not recover in ≤ 21 days, permanently discontinue binimetinib. Closely monitor LVEF until resolution or for up to 16 weeks.
Grade 3 – 4	Permanently discontinue binimetinib. Closely monitor LVEF until resolution or up to 16 weeks. Note: Copies of ECHO and/or MUGA scans could be requested for subjects to be available to the Sponsor for subjects with absolute decrease of >10% in LVEF compared to baseline and LVEF < 50% or LLN.
CK Elevation	
Grade 1-2	Maintain dose of encorafenib and binimetinib. Ensure subject is adequately hydrated. Closely monitor CK and serum creatinine. 
 If total CK ≥ 3 × ULN, measure CK isoenzymes and myoglobin in blood or urine.
Grade 3 > 5.0 - 10.0 × ULN without renal impairment (i.e., serum creatinine < 1.5 × ULN or 1.5 × baseline)	If asymptomatic, maintain dosing of encorafenib and binimetinib. Ensure subject is adequately hydrated. Monitor and measure isoenzymes and myoglobin in blood or urine and serum creatinine. If symptomatic (muscle pain/spasms/muscle weakness), maintain dosing of encorafenib and interrupt dosing of binimetinib until resolved to CTCAE Grade ≤ 1 and monitor closely, then: 
 If resolved in ≤ 21 days, maintain dose of encorafenib and resume treatment at 1 reduced dose level^b of binimetinib. If not resolved in ≤ 21 days, maintain dose of encorafenib and permanently discontinue binimetinib.

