### 15.5. ECG

Automatic corrections for QTcF will be used, whenever available. Otherwise QTcF will be calculated as  $QT / (60/HR)^{1/3}$  (rounded to the nearest integer).

Values of QTcF will be classified as following:

QTc Categories (ms)
≤450
451-480
481-500
>500

Changes from baseline of QTcF will be classified as following:

QTc change from baseline(ms)
≤30
31-60
>60

The number and percentage of patients with at least one clinically notable ECG abnormalities (see Appendix 4) will be tabulated by type of abnormalities.

Patients with clinically notable QTcF values >500 ms and changes from baseline >60 ms will be listed including the corresponding notable values and abnormality findings.

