### 15.6. MUGA/ECHOCARDIOGRAM

Left Ventricular Ejection Fraction (LVEF) abnormalities will be defined by grade according to NCI-CTCAE version 4.03. Patient will be considered as having a LVEF abnormality if the worst post-baseline value is grade 2, 3 or 4 according to the following classification (as defined in NCI-CTCAE version 4.03):

- Grade 0: Non-missing value below Grade 2
- Grade 2:  $40\% \leq \text{LVEF value} \leq 50\%$  or  $-20\% < \text{absolute change from baseline} \leq -10\%$
- Grade 3:  $20\% \leq \text{LVEF value} < 40\%$  or  $\text{absolute change from baseline} \leq -20\%$
- Grade 4: LVEF value < 20%.

The following summaries will be produced for LVEF:

- Incidence of worst post-baseline LVEF value with NCI-CTCAE version 4.03 grades.
- Shift tables using NCI-CTCAE version 4.03 grades to compare baseline to the worst post-baseline LVEF value with NCI-CTCAE version 4.03 grades.
- Time to LVEF abnormalities will be presented as KM plots if at least 10 patients with abnormality are observed. Patients with no LVEF abnormality will be censored at their last on-treatment LVEF examination date. Patients with no adequate post-baseline LVEF

assessment will be censored at their date of first study treatment administration. Two types of abnormalities will be considered:

- LVEF value < 50%;
- LVEF value < 50% and/or absolute change from baseline  $\leq$  -10% .

Different modalities to assess LVEF might be used for the same patient, change from baseline and shift table will be provided regardless of the modality.

Patients with abnormalities (grade 2 or above NCI-CTCAE version 4.03) will be tabulated in an individual listing.

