**Table 2: ECG clinically notable values or changes **

Parameter	Clinically notable values or changes
QTcF	Value in 451-480 ms Value in 481-500ms Value > 500 ms
	Increase from Baseline in 31-60 ms Increase from Baseline > 60 ms
Heart rate	HR > 100 bpm HR < 60 bpm

APPENDIX 5	TABLES, FIGURES AND LISTINGS	
-------------------	-------------------------------------	--

**The list of TFLs to be produced is displayed in the excel file: ANCHOR\_SAP\_Appendix5\_TFL.xls. Last version of this file will be used for analysis.**

*Note: Any update of this list (e.g. modification of a title) without impact on the statistical analysis described in this plan will not lead to a new version of the statistical analysis plan.*

**The stage 2 analysis (if considered as primary analysis) will include all analyses listed (except PK and Healthcare resource utilization analyses that will be performed once at the end of study).**

Each output name (.rtf) will end with the population reference (including 16.2 listings), for instance:

- Table 11\_2\_1\_1 (Demographics on ES): *T11\_2\_1\_1\_demo\_ES.RTF*
- Table 12\_1\_1\_1 (Duration of Exposure to Encorafenib on FAS): *T12\_1\_1\_1\_enco\_expos\_FAS.RTF*

Tables, figures and listings that will be performed for the subgroup of subjects in Japan separately at the time of the primary analysis (i.e. Stage 2 or at Stage 1 if study stops for futility), will have RTF reference ended with “[Population]\_JAP”. For instance:

- Table 11\_2\_1\_1 (Demographics on ES, only Japanese subjects): *T11\_2\_1\_1\_demo\_ES\_JAP.RTF*
- Table 12\_1\_1\_1 (Duration of Exposure to Encorafenib on FAS): *T12\_1\_1\_1\_enco\_expos\_FAS\_JAP.RTF*

It should be mentioned in the Titles:

- The analysis (IDSMC, Stage 1, Stage 2 or EOS),
- When analyses are performed on the subgroup of Japanese subjects

For instance, for the description of demographics characteristics performed on the FAS (Title in the TFL list is: “*Demographics [FAS]*”), Title should display:

- IDSMC analysis: “*Demographics [FAS, IDSMC x]*”
- Stage x analysis: “*Demographics [FAS, Stage x]*”

- EOS analysis: “*Demographics [FAS, EOS]*”
- Stage x analysis on the subgroup of Japanese subjects: “*Demographics – Japanese Subjects [FAS, Stage x]*”

APPENDIX 6	SIGNATURE PAGE FROM SAP V4	
-------------------	-----------------------------------	--

DocuSign Envelope ID: B5C08F10-24FF-44E8-8F4C-59E2B059FDAB0

Confidential

W00090 GE 2 01

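### SAP 15.5 counts QTcF of 451–480 ms and ECG heart-rate limits as notable with no post-baseline or worsening condition, so values already present at entry are counted; SAP 15.6 also treats an LVEF of exactly 50% in two ways

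*Protocol*

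**What the plan says.** **Entry limits.** Protocol 5.1, criterion 13, has a first item beginning "Left ventricular ejection fraction (LVEF", which requires an LVEF of at least 50%, and a second requiring a mean triplicate "formula (QTcF) value ≤ 480 msec". Criterion 13 sets no heart-rate limit.

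**ECG.** SAP 15.5 tabulates, by type, "The number and percentage of patients with at least one clinically notable ECG abnormalities". The types are in Appendix 4 Table 2. The first QTcF entry is "Value in 451-480 ms", followed by 481–500 ms and above 500 ms. Increases from baseline of 31–60 ms and above 60 ms are further, separate types. Heart rate is notable above 100 or below 60 bpm. None of the absolute limits carries a post-baseline or change condition. SAP 15.5 also classifies QTcF values and QTcF changes, each on its own, and lists subjects above 500 ms or with a rise above 60 ms.

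**LVEF.** SAP 15.6 states: "Patient will be considered as having a LVEF abnormality if the worst post-baseline value is grade 2, 3 or 4". Grade 2 is met by a value from 40% to 50% inclusive, or by an absolute fall of at least 10 and less than 20 points. Incidence by worst grade, a baseline-to-worst shift table and a listing of Grade 2 or above are planned. The Kaplan-Meier plot uses two definitions: LVEF below 50%, and LVEF below 50% and/or a fall of 10 points or more. It is drawn only if at least 10 patients have an abnormality.

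**The concern.** The trial has one arm, so no control rate lets a reader subtract pre-existing values from a count of notable ECG findings. Criterion 13 admits the whole 451–480 ms band, so that row of the table mixes subjects who entered it on treatment with subjects who were in it from the start.

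Elsewhere the SAP guards against this:

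- Appendix 4 Table 1 requires both a value and a change from baseline for systolic pressure, diastolic pressure and heart rate.
- SAP 15.10 counts only newly occurring eye abnormalities, for example in fundoscopy and slit lamp.
- Treatment-emergent adverse events in SAP 15.2 must occur or worsen in the treatment period, apart from late related serious events.

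Heart rate even has two rules in one appendix. Table 1 needs 120 bpm or more, or 50 bpm or less, with a change of at least 15 bpm. Table 2 needs only more than 100 or less than 60 bpm.

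For LVEF the issue is narrower: one term, two boundaries, and therefore outputs that can classify the same subject differently.

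**Working it through.** The plan states no figure for this point, so there is none to reproduce. The check applies the SAP rules to chosen values and sees where each subject lands.

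**QTcF.** Inputs: the entry limit of 480 ms (criterion 13); the value bands and increase bands (Appendix 4 Table 2). Change = on-treatment value − baseline.

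| Baseline → on treatment (ms) | Within entry limit | Change (ms) | Increase row | Value row |
|---|---|---|---|---|
| 450 → 450 | yes | 0 | none | none |
| 451 → 451 | yes | 0 | none | 451–480 |
| 465 → 465 | yes | 0 | none | 451–480 |
| 480 → 480 | yes | 0 | none | 451–480 |
| 450 → 465 | yes | 465 − 450 = 15 | none (≤30) | 451–480 |
| 481 → 481 | no | – | – | – |

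The overlap with the entry limit is the entire band. The third and fifth rows show why the separate increase types do not resolve it. The unchanged subject and the subject who moved into the band on treatment make the same contribution: one count in the value row, none in any increase row.

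**ECG heart rate.** A subject just under 60 or just over 100 bpm at baseline who stays there is counted, because Table 2 has no change condition.

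**LVEF.** Inputs: the entry limit of 50%; the SAP 15.6 grade limits; the two Kaplan-Meier definitions. All rows are eligible.

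| Baseline → worst (%) | Change | SAP grade | Incidence and listing | KM: <50% | KM: <50% and/or change ≤ −10 |
|---|---|---|---|---|---|
| 50 → 50 | 0 | 2 | counted | no event | no event |
| 50.1 → 50.1 | 0 | 0 | not counted | no event | no event |
| 55 → 55 | 0 | 0 | not counted | no event | no event |
| 55 → 50 | 50 − 55 = −5 | 2 | counted | no event | no event |

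The overlap with the entry limit is the single value 50%. The last row shows that the two boundaries also part company for a subject who has worsened. A worsening condition alone would therefore not reconcile the outputs. The 10-patient trigger for the plot is also left open, since the section does not say which definition of abnormality it uses.

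**Size.** The documents give no baseline distribution of QTcF, heart rate or LVEF, so the number affected cannot be computed. At the target of 90 subjects, each pre-existing case adds 1/90 = 1.1 percentage points to its row, or slightly less if the Full Analysis Set is larger.

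**The case against.** The strongest reply is that baseline is not ignored. SAP 15.6 plans a shift table in which a subject unchanged at 50% appears as Grade 2 to Grade 2. Worst grade plus shift table is also the SAP's convention for graded laboratory data. This stands, and it makes the LVEF part minor. The SAP also attributes its Grade 2 limit to CTCAE v4.03, so the limit itself need not be in error. The Kaplan-Meier section does announce its own definitions, but it still censors patients with no LVEF abnormality under a term the section has already defined differently.

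For QTcF, the reply is that increases from baseline sit in the same table, that thresholds follow cited guidance, and that individual listings exist. The first does not answer the point, because the rows are separate counts and cannot be crossed. The second concerns where the bands lie, not who is counted in them. The third stands: the information can be recovered by hand.

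It is also fair that the internal contrast is not uniform. Body temperature in Appendix 4 Table 1 has no change condition either.

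Finally, a QTcF shift table may exist. Protocol 13.9.4 allows shift tables for ECG if applicable, and the list of outputs is in a separate file. What can be said is that the SAP text does not specify one. SAP section 20 also records that over-time safety analyses were removed, so the protocol's by-time summaries cannot be assumed to fill the gap.

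**Conclusion.** The ECG point holds. As written, the counts for QTcF 451–480 ms and for ECG heart rate include subjects whose value has not changed since entry, and no table specified in the SAP text separates them. The LVEF point holds only as an inconsistency at 50% and a count that ignores the baseline grade at that one value. The effect is confined to descriptive safety tables; the primary endpoint and its test are untouched, and SAP section 8 already makes everything else exploratory.

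A reader might infer more than the documents support:

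- **That the plan ignores baseline altogether.** It does not: LVEF has a shift table and QTcF change is classified.
- **That criterion 13 is at fault.** It is not; the issue lies in the counting rules.
- **That Protocol Table 14 contradicts the SAP.** Its rule, "If the LVEF recovers (defined as LVEF" at least 50% or the lower limit of normal, also limits the fall from baseline. It governs dosing, not analysis.
- **That a material share of subjects is affected, or that the count can be set against the ejection-fraction-decreased rate in Protocol Table 4, (20 + 10)/269 = 11.2%.** The first has no basis in the documents. The second compares a reported adverse-event term with a measured grade.

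**What to change.** **SAP 15.5 and Appendix 4 Table 2.** Count a QTcF band only when a post-baseline value lies in a worse band than the baseline defined in SAP 9.4 (the pre-dose triplicate mean on Cycle 1 Day 1). Count an ECG heart-rate limit only when a post-baseline value crosses it and baseline did not already lie beyond it on the same side. As an alternative or in addition, specify a baseline-to-worst post-baseline QTcF shift table using the four value categories already in SAP 15.5.

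**SAP 15.6.** Treat 50% the same way in the incidence table, the listing and the Kaplan-Meier definitions, and say which definition triggers the plot. Count and list an LVEF abnormality only when the worst post-baseline grade is worse than the baseline grade. Keep the planned shift table.

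**Cost.** SAP wording and a programming condition on data already collected. Reported rates may be slightly lower. No grade limit, assessment or clinical rule needs to change.

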5.2. EXCLUSION CRITERIA

1. Prior systemic therapy for metastatic disease.

Note: previous adjuvant/neoadjuvant therapy is allowed provided that 1) the interval from the end of chemotherapy to relapse is >6 months OR 2) in the case of neoadjuvant therapy, complete surgical resection was achieved and the interval from the end of chemotherapy to relapse is >12 months. Prior locoregional radiotherapy is allowed.

2. Prior treatment with any RAF inhibitor, MEK inhibitor, cetuximab or other anti-EGFR treatment.

3. Symptomatic brain metastasis.

Note: subjects previously treated or untreated for these conditions who are asymptomatic in the absence of corticosteroid and anti-epileptic therapy are allowed. Brain metastases must be stable for ≥ 4 weeks with imaging (e.g. brain magnetic resonance imaging [MRI] or computed

tomography [CT] demonstrating no current evidence of progressive brain metastases at screening).

4. Leptomeningeal disease.
5. History or current evidence of Retinal Vein Occlusion (RVO) or current risk factors for RVO.

Note: Risk factors for RVO are uncontrolled glaucoma or ocular hypertension, history of hyperviscosity syndrome or hypercoagulability syndrome.

6. Use of any herbal medications/supplements or any medications or foods that are moderate or strong inhibitors or inducers of CYP3A4/5 \leq 1 week prior to the start of treatment.

Note: However, subjects who either discontinue moderate or strong inhibitors or inducers of CYP3A4/5 or switch to another medication at least 7 days prior to starting study treatment are eligible.

7. Known history of acute or chronic pancreatitis within 6 months prior to the start of the treatment.
8. History of chronic inflammatory bowel disease or Crohn's disease requiring medical intervention (immunomodulatory or immunosuppressive medications or surgery) \leq 12 months prior to first dose.
9. Impaired cardiovascular function or clinically significant cardiovascular diseases, including any of the following:
 - i. *History of acute myocardial infarction, acute coronary syndromes (including unstable angina, coronary artery bypass graft (CABG), coronary angioplasty or stenting) \leq 6 months prior to start of study treatment.*
 - ii. *Symptomatic congestive heart failure (Grade 2 or higher), history or current evidence of clinically significant arrhythmia and/or conduction abnormality \leq 6 months prior to start of study treatment, except rate controlled atrial fibrillation and paroxysmal supraventricular tachycardia.*
10. Uncontrolled hypertension defined as persistent elevation of systolic blood pressure \geq 150 mmHg or diastolic blood pressure \geq 100 mmHg despite optimal therapy.
11. Impaired hepatic function, defined as Child-Pugh class B or C.

12. ~~Known history of Gilbert's syndrome or is known to have any of the following genotypes: UDP glucuronosyl transferase (UGT)1A1*6/*6, UGT1A1*28/*28, or UGT1A1*6/*28. No more applicable from Protocol V6.0/Amendment PA03~~
13. Impaired gastrointestinal function or disease* which may significantly alter the absorption of encorafenib or binimetinib or recent changes in bowel function suggesting current or impending bowel obstruction.
- *eg. ulcerative diseases, uncontrolled nausea, vomiting, diarrhea, malabsorption syndrome, small bowel resection.*
14. Previous or concurrent malignancy* within 5 years of study.
- *except cured basal or squamous cell skin cancer, superficial bladder cancer, prostate intraepithelial neoplasm, carcinoma in-situ of the cervix or any other malignancy that has been adequately treated and has not recurred within 3 years prior to study entry.*
15. History of thromboembolic* or cerebrovascular events** ≤ 6 months prior to starting study treatment.
- *excluding venous thrombosis related to indwelling catheters and treated with low-grade anticoagulants*
***including transient ischemic attacks, cerebrovascular accidents, deep vein thrombosis or pulmonary emboli.*
16. Concurrent neuromuscular disorder that is associated with the potential of elevated Creatine Kinase (CK).
- Note: e.g. inflammatory myopathies, muscular dystrophy, amyotrophic lateral sclerosis, spinal muscular atrophy.*
17. Residual CTCAE ≥ Grade 2 toxicity from any prior anticancer therapy, with the exception of Grade 2 alopecia or Grade 2 neuropathy.
18. Known history of human immunodeficiency virus (HIV) infection.
- Note: HIV testing will only be conducted in jurisdictions specifically requiring it.*
19. Active hepatitis B or hepatitis C infection.
20. Known contraindication to receive cetuximab at the planned doses. Refer to the most recent cetuximab summary of product characteristics (SPC) or local label as applicable.

21. Subjects who have any medical condition that would, in the Investigator's judgment, prevent the subject's participation in the clinical study due to safety concerns or compliance with study procedures.
22. Any medical or psychiatric condition or laboratory abnormality that may increase the risk with study participation or study drug administration or that may interfere with the interpretation of study.
23. Pregnancy, confirmed by a positive human chorionic gonadotropin (hCG) laboratory test result, or breastfeeding.
24. Is a family member of the Investigator or any associate, colleague, or employee assisting in the conduct of the study (secretary, nurse, technician).
25. Is in a position likely to represent a conflict of interest.
26. Participation in a clinical study with administration of an investigational product within 4 weeks or five times the half-life of the investigational product, whichever is longer, before the first dose of study treatment.
27. Is mentally unable to understand the nature, objectives and possible consequences of the trial; or he/she refuses to its constraints.

